14.6.2. Study Population

Age

 Age will be calculated based on the date of first dose. Only year of birth is collected on the eCRF, therefore day and month of birth are imputed as '30JUN' in order to derive age. Birth date will be presented in listings as 'YYYY'.
Body Mass Index (BMI)

 Calculated as Weight (kg) / [Height (m)²]
Extent of Exposure

 Number of days of exposure to study drug will be calculated based on the formula: Duration of Exposure in Days = min(Last infusionDate+20, Death date) – First infusion Date + 1 Participants who were enrolled but did not report a treatment start date will be categorised as having zero days of exposure. The cumulative dose will be based on the formula: Cumulative Dose (mg/kg) = Sum of Dose at Each Cycle Dose intensity will be calculated based on the formula: Dose intensity (mg/kg/3 week) = Cumulative Dose/((last infusion date – first infusion date + 21)/21)

14.6.3. Efficacy

Objective Response Rate ORR

 ORR will be calculated based on the formula: ORR = Number of Participants with a Confirmed Partial Response (PR) or Better / Number of Participants in All Treated Population

14.6.4. Safety

Adverse Events of Special Interest (AESI)

• AESI includes corneal events, thrombocytopenia and infusion related reactions
Laboratory Parameters

• If a laboratory value which is expected to have a numeric value for summary purposes, has a non-detectable level reported in the database, where the numeric value is missing, but typically a character value starting with '<x' or '>x' (or indicated as less than x or greater than x in the comment field) is present, the number of significant digits in the observed values will be used to determine how much to add or subtract in order to impute the corresponding numeric value.• Example 1: 2 Significant Digits = '< x' becomes $x - 0.01$• Example 2: 1 Significant Digit = '> x' becomes $x + 0.1$• Example 3: 0 Significant Digits = '< x' becomes $x - 1$

14.6.5. Pharmacokinetic

PK

• Plasma sample analysis will be performed under the control of GSK Bioanalysis Immunogenicity and Biomarkers (BIB) group, the details of which will be included in the Study Reference Manual (SRM). Belantamab mafodotin, total antibody, and cys-mcMMAF plasma concentrations will be determined using the currently validated methodology. The actual sampling times, if different from protocol, will be used in the PK calculations. Please refer to the rules in Section 14.7.2 for the plasma concentrations below Limit of quantification (LOQ).• Belantamab mafodotin, total antibody, and cys-mcMMAF plasma concentration-time data will be analyzed by non-compartmental methods with WinNonlin 6.3 or above and derived PK parameters will be summarised and listed. Derived Pharmacokinetic parameters will be summarized by cycle and dose level. Mean, standard deviation, median, minimum, maximum, geometric mean, and the standard deviation, CV%, and 95% CI of parameters values will be provided; Individual concentration, linear and semi-logarithmic individual concentration-time profiles, and mean and median profiles (when appropriate) will be provided.

14.7. Appendix 7: Reporting Standards for Missing Data

14.7.1. Premature Withdrawals

Element	Reporting Detail
General	
 Participant study completion (i.e. as specified in the protocol) was defined as completed all scheduled visit and completed exit visit. All available data from participants who were withdrawn from the study will be listed and all available planned data will be included in summary tables and figures, unless otherwise specified. The Withdrawal visit will be slotted as per Appendix 3: Assessment Windows or will be summarised as the withdrawal visit.

14.7.2. Handling of Missing Data

Element	Reporting Detail																								
General	
 Missing data occurs when any requested data is not provided, leading to blank fields on the collection instrument: 
 These data will be indicated by the use of a “blank” in participant listing displays. Unless all data for a specific visit are missing in which case the data is excluded from the table. Answers such as “Not applicable” and “Not evaluable” are not considered to be missing data and should be displayed as such. 																								
Outliers	
 Any participants excluded from the summaries and/or statistical analyses will be documented along with the reason for exclusion in the clinical study report. 																								
PK	
 Concentrations which are below the LLQ (“lower limit of quantification” for the analyte in question) are listed as NQ in the raw concentration data provided by DMPK. Several derived variables exist for the imputation of these concentrations. The following variables exist in the PKCNC dataset for different imputations of the raw concentration data: 
 PCORRES: Original result PCSTRESPN: Original result in standard units PCSTIMPN: Imputed result for use in the calculation of summary statistics PCSTIMSN: Imputed result for individual concentration plots PCWNLN: Imputed result for use in WinNonlin analysis The imputation of NQs for variables in the PKCNC file will be based on that defined in GUI_51487, under the section “How to Handle Values Below the Quantification Limit”. A brief summary is provided in the table below. 
  
 Variable	Leading NQ	Single NQ between measurable concentrations	More than one consecutive NQ between measurable concentrations	Measurable concentrations after more than one consecutive mid-profile NQ*	Trailing NQ (consecutive NQs in the tail)	
   
 PCSTIMPN	0	NULL	0	NULL	0	
 
 PCSTIMSN	0	NULL	0	No Action	NULL	
 
 PCWNLN	0	NULL	NULL	NULL	NULL	
  
	Variable	Leading NQ	Single NQ between measurable concentrations	More than one consecutive NQ between measurable concentrations	Measurable concentrations after more than one consecutive mid-profile NQ*	Trailing NQ (consecutive NQs in the tail)	PCSTIMPN	0	NULL	0	NULL	0	PCSTIMSN	0	NULL	0	No Action	NULL	PCWNLN	0	NULL	NULL	NULL	NULL
Variable	Leading NQ	Single NQ between measurable concentrations	More than one consecutive NQ between measurable concentrations	Measurable concentrations after more than one consecutive mid-profile NQ*	Trailing NQ (consecutive NQs in the tail)																				
PCSTIMPN	0	NULL	0	NULL	0																				
PCSTIMSN	0	NULL	0	No Action	NULL																				
PCWNLN	0	NULL	NULL	NULL	NULL																				

Element	Reporting Detail
	* a mid-profile NQ is defined as any NQ where measurable concentrations exist both before and after that NQ in the profile

14.7.2.1. Handling of Missing and Partial Dates

Element	Reporting Detail
General	
 Partial dates will be displayed as captured in participant listing displays. Imputed partial dates will not be used to derive study day, duration (e.g. duration of adverse events), or elapsed time variables. In addition, imputed dates are not used for deriving the last contact date in the overall survival analysis dataset. Imputed dates will not be displayed in listings. However, where necessary, display macros may impute dates as temporary variables for the purpose of sorting data in listings only. In addition, partial dates may be imputed for 'slotting' data to study time periods or for specific analysis purposes as outlined below.
Adverse Events	
 The eCRF allows for the possibility of partial dates (i.e., only month and year) to be recorded for AE start and end dates; that is, the day of the month may be missing. 
 Missing Start Day: First of the month will be used unless this is before the start date of study treatment; in this case the study treatment start date will be used and hence the event is considered On-treatment as per Appendix 4: Study Phases and Treatment Emergent Adverse Events. Missing Stop Day: Last day of the month will be used. Completely missing start dates will remain missing, with no imputation applied. Consequently, time to onset and duration of such events will be missing. Completely missing end dates will remain missing, with no imputation applied. Consequently, duration of such events will be missing.
Concomitant Medications/Medical History	
 Partial dates for any concomitant medications recorded in the CRF will be imputed using the following convention: 
 If the partial date is a start date, a '01' will be used for the day and 'Jan' will be used for the month If the partial date is a stop date, a '28/29/30/31' will be used for the day (dependent on the month and year) and 'Dec' will be used for the month. The recorded partial date will be displayed in listings.
Covariates for efficacy analysis (Date of initial diagnosis/ Last recurrence/ Last progression)	
 If both month and day are missing, first of January will be used If only day is missing, first of the month will be used
Treatment end date	
 If there is more than one study treatment, imputation of missing treatment end date will be applied to all applicable treatments following rules below and treatment end date is the latest treatment end date across all study treatments. In general, completely missing end dates are not imputed, with the following exceptions for imputation of missing treatment end date at interim analyses. For imputation of missing exposure end date at an interim analysis when participants are still on treatment, the following conventions will be applied:

Element	Reporting Detail
	
○ If the missing end date is in the last exposure record, the earliest of: the date of the data cut-off, the date of withdrawal from the study, or the death date will be used○ If the missing end date is not in the last exposure record, treatment start date for the record will be used● The imputed treatment end date will be used to calculate cumulative dose and duration of treatment as specified in Section 14.6.2.● If treatment end date is missing for a cycle, treatment start date for the cycle will be used.

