Serum immunofixation	Х						At time of CR or suspected PD after CR or sCR	At time of CR or suspected PD after CR or sCR	At time of CR or suspected PD after CR or sCR
Serum Kappa, lambda free LC, FLC ratio	X						X every 3 weeks	Х	X
Calcium corrected for albumin (serum)	Х						X every 3 weeks	X	X
IgG, IgM, IgA	Х	Х					X every 3 weeks	Х	Х
IgD/E ²⁸	Х	Χ					X every 3 weeks	Х	Х
					Bone Marro	w Aspiration	/ biopsy		
FISH testing on bone marrow ²⁹	Χ								
CCI									
BM for disease assessment ³¹	X						At the time of CR (always) or at time of suspected PD (only if not evident otherwise)	Only if CR has been achieved by this visit, or suspected PD not evident otherwise	Only if CR has been achieved by this visit, or suspected PD not evident otherwise
Bone marrow to assess sCR by (IHC) ³²							X ³²	Only if CR has been achieved on this visit.	Only if CR have been achieved on this visit
					Biomarker				
CCI									
				Stu	ıdy treatmer	nt			
Premedication if needed		Х					Х		
Belantamab mafodotin administration ³⁴		Х					Х		
Preservative-free artificial tears ³⁵		Х					Everyday until end of Study treatment		
Adverse Events ³⁶		Х	Χ	X	Х	Χ	X		

		Cycle 1	Cycle 1	Cycle 1	Cycle 1	Cycle 1	Treatment Period ³ Cycle = 21 days	End of	55 5 11 5
Study Assessments	Screen ¹	Day 1 ²	Day 2	Day 4	Day 8	Day 15	D1 of C2 - CX	Treatment Follow-up ⁴	PD Follow-up ⁵
Concomitant Medications	Х	Х	X		Х	Х	X		
Health Outcomes									
OSDI ³⁷	Χ	Χ					X every 3 weeks	Χ	Χ

Abbreviations:

ADA = Anti-drug Antibody; ALP = alkaline phosphatase; BM = bone marrow; BNP = B-type natriuretic peptide; BP = blood pressure; C1D1 = Cycle 1 Day 1, etc.; CK = creatine kinase; CRP = C-reactive protein; EM = extramedullary; EOI = End of Infusion; FISH = fluorescence in situ hybridization; FLC = free light chain; HR= heart rate; Ig = immunoglobulin; PK = Pharmacokinetics; QID = 4 times a day; SOI = start of infusion; SPEP = serum protein electrophoresis; UPEP = urine protein electrophoresis; OSDI = Ocular Surface Disease Index

- 1. All Screening assessments must be performed within 21 days prior to first dose unless otherwise specified. Informed Consent must be signed before any study-specific assessments are performed. Screening Assessment do not need to be repeated on C1D1 unless otherwise specified.
- 2. Assessments scheduled on days of dosing must be done prior to drug administration, unless otherwise specified. All other assessments can be done ±3 days unless otherwise specified.

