8.3.1. Time Period and Frequency for Collecting AE and SAE Information

- All SAEs will be collected from signing of the ICF until 70 days following discontinuation of study treatment regardless of initiation of a new cancer therapy or transfer to hospice at the time points specified in the SoA (Table 1). However, any SAEs assessed as related to study participation (e.g., study intervention, protocol-mandated procedures, invasive tests, or change in existing therapy) or related to a GSK product will be recorded from the time a participant consents to participate in the study up to and including follow up.
- All AEs will be collected from the start of treatment until 70 days following discontinuation of study treatment regardless of initiation of a new cancer therapy or transfer to hospice at the time points specified in the SoA.
- Medical occurrences that begin before the start of study treatment but after obtaining informed consent will be recorded on the Medical History/Current Medical Conditions section of the electronic case report form (eCRF) not the AE section.
- All SAEs will be recorded and reported to the sponsor or designee immediately and under no circumstance should this exceed 24 hours, as indicated in Appendix 3. The investigator will submit any updated SAE data to the sponsor within 24 hours of it being available.
- Investigators are not obligated to actively seek AEs or SAEs in former study participants. However, if the investigator learns of any SAE, including a death, at any time after a participant has been discharged from the study, and he/she considers the event to be reasonably related to the study treatment or study participation, the investigator must promptly notify the sponsor.

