14.4.2. Treatment Emergent Flag for Adverse Events

Flag	Definition
Treatment Emergent	
• Study Treatment Start Date ≤ AE Start Date ≤ Study Treatment Stop Date + 70 days.

NOTES:

- If the study treatment stop date is missing, then the AE will be considered to be On-Treatment.
- Time of study treatment dosing and start/stop time of AEs should be considered, if collected.

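### The adverse-event partial-date rule puts events from months that ended before the first dose On-treatment

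*SAP*

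**What the plan says.** SAP 14.7.2.1 starts from the fact that days can be missing: "The eCRF allows for the possibility of partial dates (i.e., only month and year) to be recorded for AE start and end dates". For a missing start day the rule is "First of the month will be used unless this is before the start date of study treatment". Where that first-of-month date is earlier than the first dose, the SAP replaces it with the date of first dose and, citing its Appendix 4, treats the event as On-treatment. A missing stop day becomes the last day of its month.

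The treatment-emergent flag in SAP 14.4.2 includes the first-dose date itself: "Study Treatment Start Date ≤ AE Start Date ≤ Study Treatment Stop Date + 70 days". SAP 14.4.1 sets the general principle that an event is placed on-treatment by default only when its timing cannot be determined.

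On collection, Protocol 8.3.1 says "All SAEs will be collected from signing of the ICF until 70 days following discontinuation of study treatment". A later bullet of the same section says "Medical occurrences that begin before the start of study treatment but after obtaining informed consent will be recorded on the Medical History/Current Medical Conditions" page, and not among the adverse events. Footnote 36 of the Schedule of Activities repeats that related SAEs are collected from consent.

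**The concern.** The rule compares the first of the recorded month with the treatment start date and tests nothing else. It does not ask whether the recorded month is the month in which treatment started, or whether a recorded stop date falls before treatment.

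Within the treatment-start month this is a sensible conservative choice, because the order of event and first dose is unknown. For an earlier month it is not: the recorded month and year show that the event began before dosing, and the rule overrides them.

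At stake is whether an event from the screening period is labelled as having emerged on study drug. In a study whose primary endpoint is adverse events and whose cohorts hold up to 6 evaluable participants, one wrong label can be visible in any display that uses it.

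**Working it through.** The plan gives no figure to reproduce. The check applies the rule literally.

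**Inputs**
- Imputation rule: SAP 14.7.2.1.
- Flag: SAP 14.4.2.
- Time before dosing: Protocol 1.3, footnote 1, "All Screening assessments must be performed within 21 days prior to first dose unless otherwise specified". Thirty days serves as an upper range, because footnotes 24 and 26 allow some imaging that early.
- Assumptions, for sizing only: every date in 2020 and 2021 is a possible treatment start (366 + 365 = 731), and every pre-dose day in the window is equally likely as onset.

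**Step 1: is the condition ever not met?** Let T be treatment start, A the true onset and M the first of A's month. For pre-treatment onset, M ≤ A < T, so M < T always. The imputed start is T, and T satisfies the flag. Every pre-treatment event with a missing start day is therefore flagged treatment-emergent, whatever the calendar.

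**Step 2: which of these are errors?** If A and T share a month, the timing cannot be told and the shift agrees with SAP 14.4.1, unless a known stop date precedes T. If A's month is earlier, the timing is known and the shift is wrong.

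**Step 3: how large is the earlier-month share?**
- 21-day window: 731 × 21 = 15,351 combinations. A treatment start on day D of a month (D = 1 to 21) has 22 − D onset days in the previous month. The sum is 21 + 20 + … + 1 = 231 per month, and 231 × 24 = 5,544. Share: 5,544 / 15,351 = 36.1%. The window reaches an earlier month for 21 × 24 = 504 of 731 start dates, or 68.9%.
- 30-day window: 731 × 30 = 21,930 combinations. Day D (1 to 30) has 31 − D such days, which sum to 465 per full month. 465 × 24 = 11,160, less 1 for February 2020 and 3 for February 2021, gives 11,156. Share: 11,156 / 21,930 = 50.9%.

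These shares are conditional on a pre-dose event with a missing day. They are not estimates of how often one occurs.

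**Step 4: an illustration.** Recorded start March, day unknown; first dose 10 April. M is 1 March, before 10 April, so the imputed start is 10 April. If the stop is also recorded only as March, it becomes 31 March, and the event ends 10 days before it begins.

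**Step 5: effect on a filtered table.** One participant is 1/6 = 16.7 percentage points, or 1/12 = 8.3, if that participant has no other event counted in the row.

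**Step 6: effect of the month condition in the fix.** Earlier-month events flagged treatment-emergent fall from 5,544 to 0 (21 days) and from 11,156 to 0 (30 days). Same-month events keep the on-treatment default: 9,807 of 15,351 (63.9%) and 10,774 of 21,930 (49.1%). The stop-date condition was not part of this count.

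**The case against.** The strongest objection is that no changed table has been shown, and it largely stands. SAP 8.4 tabulates all SAEs, and the SAE tables in SAP 14.12.10 (4.140 and 4.150) carry no treatment-emergent restriction in title or programming notes. SAP 8.2 states none for the AE tables. Without a filter, a screening-period SAE held in the AE data is tabulated whatever its imputed date. A reader might infer that a false SAE necessarily enters the SAE tables or the primary endpoint; the documents do not support that.

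Nor does one misdated event readily move the any-AE count. That needs a participant with no other AE, and Protocol 2.3.2 reports eye disorders alone in 78% of participants at 2.5 mg/kg in the global phase II study. No route to the DLT count is shown either: Protocol 4.1.2 also requires that a relationship to the agent cannot be ruled out.

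It would also be too strong to say that such records do exist. The Medical History bullet in Protocol 8.3.1 does not exempt serious events, and the adverse-event row of the protocol's Schedule of Activities has no screening mark. The SAE bullet and footnote 36 point the other way, so the records are possible but not certain.

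Further mitigations stand. SAEs are reported within 24 hours, so a missing day should be rare. Under SAP 14.7.2.1 imputed dates are not used for study day or duration, and listings show dates as captured.

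One apparent rescue fails. The default phase table in SAP 14.4.1 places a date equal to treatment start in Pre-Treatment. But SAP 14.7.2.1 says "the study treatment start date will be used and hence the event is considered On-treatment", and both the flag and the alternative phase definition, for when times are collected, include the start date.

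**Conclusion.** The rule misclassifies a missing-day event whose recorded month ended before the first dose, and it contradicts the principle in SAP 14.4.1. That follows from the text and needs no assumption. The certain error is in the treatment-emergent flag and in the study phase that SAP 14.7.2.1 assigns.

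Any effect on a table is conditional: an affected record must exist, the display must be restricted to treatment-emergent or on-treatment events, and the participant must have no other such event in the row. Then the effect is up to 16.7 percentage points with 6 participants or 8.3 with 12. Same-month events are not part of the fault, apart from those with a known stop date before treatment. That the rule was written with only the treatment-start month in mind is a reasonable inference, but the SAP does not say so.

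This is a minor correction, worth making because the written rule gives a wrong answer and is easily put right.

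**What to change.** Amend the missing-start-day rule in SAP 14.7.2.1 as follows:

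- Impute the treatment start date only when the recorded month and year equal those of treatment start and no known stop date is before treatment start.
- Otherwise impute the first of the recorded month.
- Classify an event as pre-treatment if its recorded month is earlier than the treatment-start month, or if its known stop date is before treatment start.

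The last line is needed for an event recorded in the treatment-start month whose stop date precedes the first dose. Months after the treatment-start month are handled as now.

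The cost is a short change to the SAP text and the matching condition in the derivation program. No new data are needed, and the default for events of undeterminable timing is kept.
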